#### **11.1.2. Serious Adverse Event (SAE)**

Any untoward medical occurrence that at any dose:

- Results in death,
- Is life-threatening

Note: The term 'life-threatening' in the definition of 'serious' refers to any adverse drug experience [adverse event] that places the patient or subject, in the view of the Investigator, at immediate risk of death from the reaction as it occurred, i.e., it does not include a reaction that, had it occurred in a more severe form, might have caused death. [emphasis added]

- Requires inpatient hospitalization or prolongation of hospitalization  
Note: In general, hospitalization signifies that the patient or subject has been detained (usually involving at least an overnight stay) at the hospital or emergency ward for observation and/or treatment that would not have been appropriate in the physician's office or outpatient setting. Complications that occur during hospitalization are AEs. If a complication prolongs hospitalization or fulfills any other serious criteria, the event is serious. When in doubt as to whether "hospitalization" occurred or was necessary, the AE should be considered serious. Hospitalization for elective treatment of a pre-existing condition that did not worsen from baseline is not considered an AE.
- Results in persistent or significant disability/incapacity  
Note: The term disability means a substantial disruption of a person's ability to conduct normal life functions.  
OR
- Is a congenital abnormality/birth defect.

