16. Medical history that includes any condition, or requires the use of concomitant medications which, in the Investigator's judgment, are associated with or create a risk of increased carotid sinus sensitivity, symptomatic bradycardia, or syncopal episodes.

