### **11.1. Definitions**

The following definitions of terms are guided by the ICH and the US CFR and are included here verbatim.

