## **11.2. Adverse Event Reporting Requirements**

### **11.2.1. Serious Adverse Events**

All events meeting the criteria for Serious Adverse Events (see [Section 11.1.2](#)) must be reported by investigational sites within 24-hours of becoming aware of the event. In order to determine the timeline for notifying the appropriate regulatory authorities and investigators, an event term, serious criteria, and causality is required at the time of the initial report. Specific SAE reporting instructions are provided in the SAE Report Completion Guidelines.

The Investigator is responsible for notifying the IRB/IEC/REB in writing of serious events as soon as is practical in accordance with the policy of the IRB/IEC/REB.

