**Table 4: Adverse Event Severity**

Grade	Criteria 
Mild – Grade 1	Asymptomatic or mild symptoms; clinical or diagnostic observations only; intervention not indicated
Moderate – Grade 2	Minimal, local, or noninvasive intervention indicated; limiting age-appropriate instrumental ADL 
Severe – Grade 3	Severe or medically significant but not immediately life-threatening; hospitalization or prolongation of hospitalization indicated; disabling; limiting self-care ADL 
Life Threatening – Grade 4	Life-threatening consequences; urgent intervention indicated
Death – Grade 5	Death related to adverse event

 A semi-colon indicates ‘or’ within the description of the grade.

 Instrumental ADL refer to preparing meals, shopping for groceries or clothes, using the telephone, managing money, etc.

 Self-care ADL refer to bathing, dressing and undressing, feeding self, using the toilet, taking medications, and not bedridden.

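### The SAE definition stops at five criteria with none for a medically important event, so some infusion events treated on site would be counted as AEs only, without the SAE label or 24-hour notice

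*Combined protocol and SAP*

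**What the plan says.** Section 11.1 introduces the definitions with the statement "The following definitions of terms are guided by the ICH and the US CFR and are included here verbatim". Section 11.1.2 then gives five criteria for seriousness:

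1. "Results in death".
2. Life-threatening. A note restricts this to a subject who, in the investigator's view, is "at immediate risk of death from the reaction as it occurred, i.e., it does not include a reaction that, had it occurred in a" worse form, might have been fatal.
3. "Requires inpatient hospitalization or prolongation of hospitalization". A note describes this as detention, usually at least overnight, at a hospital or emergency ward for care that an office or outpatient clinic could not suitably give. Doubt about whether hospitalization occurred or was needed is resolved as serious.
4. Persistent or significant disability or incapacity.
5. "Is a congenital abnormality/birth defect".

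The word OR stands before the fifth item, and nothing follows it.

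Section 11.2.1 says that events meeting these criteria "must be reported by investigational sites within 24-hours of becoming aware of the event", and that the first report must state which serious criterion applies. Section 11.2.2 makes an AE an SAE only if it meets serious criteria. Section 5.2 names SAEs alongside AEs in the primary endpoint.

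**The concern.** A list of this kind normally does two jobs: it decides what is counted as serious, and it decides what the sponsor hears about within a day. Here both jobs rest on five outcomes. An event that was prevented from reaching one of those outcomes because staff intervened in time has no criterion to meet.

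The protocol is alert to acute haemodynamic events around the infusion. Section 9.1 makes hypotension of Grade 2 or above, within 2 hours of starting the infusion, a trigger for dose reduction. Exclusion criterion 16 keeps out patients with conditions or medications that carry a "risk of increased carotid sinus sensitivity, symptomatic bradycardia, or syncopal episodes", and criterion 15 and the prohibited-medication list in 8.9.1 deal similarly with sharp falls in blood pressure. Events of this type can be treated on the spot, so they are the ones most likely to fall between the criteria.

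Safety is the primary objective. What is at stake is the completeness of the SAE count and the speed with which the sponsor learns of such events.

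**Working it through.** **1. The plan's own safety figure.** Section 12.2 says that 300 subjects give a 95% probability of seeing an adverse event of 1% true incidence at least once. With n = 300 and p = 0.01:

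P(at least one) = 1 − (1 − p)^n = 1 − 0.99^300 = 0.951.

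The figure reproduces. It concerns adverse events, not SAEs, so the definition in 11.1.2 does not alter it.

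**2. Tracing one event through the list.** Take a subject who has hypotension, bradycardia or syncope at the infusion visit, is treated there, recovers and goes home.

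| Criterion in 11.1.2 | Met? |
|---|---|
| Death | No |
| Life-threatening | No, unless the investigator sees immediate risk of death from the event as it happened; the possibility of a worse form is ruled out by the note |
| Hospitalization or prolongation | No, if the care was suitable for an outpatient setting and nobody doubts it; yes if there is doubt |
| Disability or incapacity | No |
| Congenital abnormality | No |

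So the gap consists of events with no immediate risk of death and no doubt about hospitalization.

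**3. Searching for a criterion elsewhere.** The nearest wording is the Grade 3 row of Table 4, "Severe or medically significant but not immediately life-threatening". That is a severity grade and does not make an event serious. Section 11.5 mentions medical events that the investigator considers serious, but in the setting of data collected beyond 30 days, and it adds nothing to the list in 11.1.2.

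**4. What follows for the traced event.**

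| Step | Treatment under the plan |
|---|---|
| Recording (11.2.2, 11.4) | Recorded on the CRF with grade, relationship and action taken |
| Tabulation (12.4) | In the treatment-emergent table; also in the severe and related tables where those apply |
| SAE part of the primary endpoint (5.2) | Not counted |
| Detailed listing (12.4) | Not included, unless it led to withdrawal |
| 24-hour report (11.2.1) | Not required; no serious criterion to enter |
| Expedited reporting (11.7) | Lacks the serious label that a SUSAR needs |

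**5. Size.** The documents give no rate for such events and no share that would escape the five criteria. As an illustration only, suppose a medically important event type has a true incidence of 1% and a share f of its cases meets the five criteria. In 70 subjects, the chance of at least one case labelled SAE is 1 − (1 − 0.01f)^70:

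- f = 1: 50.5%
- f = 0.75: 41.0%
- f = 0.5: 29.6%
- f = 0.25: 16.1%

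Both the 1% applied to this event type and the values of f are assumptions. The chance of at least one case recorded as an AE stays at 50.5% throughout.

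**The case against.** The best reply is that little is lost. Every AE is recorded whatever its severity or relationship, and 12.4 tabulates severe and treatment-related events as well as serious ones. Electronic CRFs are reviewed by monitors at regular intervals (13.1). This is right about capture. It does not answer the loss of the SAE label and of mandatory 24-hour notice.

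A second reply is that 11.1.2 has some give. Threat to life is the investigator's judgment, emergency-ward observation can count as hospitalization, and doubt about hospitalization resolves to serious. This also stands, and it narrows the gap to the class described above.

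Third, the SAE Report Completion Guidelines might contain the missing criterion. They are not among the documents, and 11.2.1 ties reporting to the list in 11.1.2.

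A reader might infer several stronger things that the documents do not support:

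- *That a 1% signal in the 300-subject database is lost.* The detection statement is about AEs. This study supplies at most 70 of the 300, which at 1% is 0.7 of 3 expected subjects, and the SAE definitions of the other studies are not shown.
- *That the protocol declares syncope and bradycardia to be effects of GC4419.* Exclusions 15 and 16 and the prohibited list concern other drugs or conditions that create risk. Only hypotension is named in the 9.1 trigger, and Sections 4.2 and 6.2.1 report safety at 90 mg similar to placebo in the Phase 2b study.
- *That these events are Grade 3 under Table 4.* Section 11.2.5 applies Table 4 only where CTCAE does not address the event, and the CTCAE text is only linked.
- *That expedited reporting is closed to them.* Section 11.7 also refers to ICH guidelines and national and local regulations.
- *That the list departs from ICH or the CFR.* Neither source is in the documents, so this cannot be settled here.

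**Conclusion.** The point holds as a narrow gap in classification and urgent reporting. Section 11.1.2 has no criterion for a medically important event, no other section supplies one, and the SAE count and the 24-hour rule both depend on that list. Events treated on site, with no immediate risk of death and no doubt about hospitalization, would appear as AEs only.

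AE capture, AE grading and the 95%-in-300 statement are unaffected. The number of events concerned cannot be estimated from the documents, and the conclusion does not depend on any assumed rate. It rests on reading 11.1.2 as a closed list, which its layout and the wording of 11.2.1 and 11.2.2 support, and on the unseen completion guidelines not widening it. In a study whose primary objective is safety, the correction is worth making because it is so cheap.

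**What to change.** Add a sixth criterion to 11.1.2: an event that, in the investigator's judgment, is medically important and may require intervention to prevent one of the listed outcomes. Check the whole list against the ICH and CFR text that Section 11.1 says it reproduces. Carry the criterion through to 11.2.1, the SAE Report Completion Guidelines and the SAE tables and listings in 12.4. Whether to give illustrative examples, and which, is for the sponsor to decide.

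This changes classification and reporting only, not dosing or clinical care. It costs one bullet and a guideline edit, a few more SAE forms for sites, and possibly a slightly higher reported SAE rate.

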## **11.2. Adverse Event Reporting Requirements**

### **11.2.1. Serious Adverse Events**

All events meeting the criteria for Serious Adverse Events (see [Section 11.1.2](#)) must be reported by investigational sites within 24-hours of becoming aware of the event. In order to determine the timeline for notifying the appropriate regulatory authorities and investigators, an event term, serious criteria, and causality is required at the time of the initial report. Specific SAE reporting instructions are provided in the SAE Report Completion Guidelines.

The Investigator is responsible for notifying the IRB/IEC/REB in writing of serious events as soon as is practical in accordance with the policy of the IRB/IEC/REB.

### **11.2.2. Collection Period for AEs and SAEs**

Any adverse medical condition or laboratory abnormality with an onset date prior to the date and time the subject received his/her first dose of study drug, GC4419, is considered pre-existing in nature and should be recorded as part of the subject's medical history. An adverse medical condition that begins on or after the first dose of study drug will be considered an adverse event, and will be considered an SAE if it meets serious criteria. AEs and SAEs will be followed for 30 days after the last dose of IMRT, cisplatin, or GC4419 (i.e., whichever occurs last), hereafter referred to as the "30-Day Follow-up Period". Similarly, new events will be reported as AEs/SAEs if the start date is within the 30-Day Follow-up Period. Increases in toxicity grade of pre-existing conditions that occur on or after the first study drug administration are also considered adverse events.

All adverse events must be recorded in the subject's source documents and on the CRF regardless of frequency, severity (grade) or assessed relationship to therapy. Additionally, SAEs must be submitted to the Safety vendor within 24 hours of awareness.

### **11.2.3. Clinical Laboratory Abnormalities and Other Abnormal Assessments as AEs and SAEs**

Clinically significant abnormal laboratory findings or other abnormal assessments that are associated with the disease being studied, unless judged by the Investigator as more severe than expected for the subject's condition, or that are present or detected at the time of enrollment and prior to study drug dosing that do not worsen, will not be reported as AEs or SAEs.

Laboratory abnormalities should only be recorded in the Adverse Event section of the CRF if at least one of the following criteria is met:

- Meets the criteria of an SAE
- Resulted in a dose reduction and/or delay in the administration of GC4419, IMRT, and/or cisplatin
- Treatment is initiated for the abnormality
- Investigational product was discontinued
- Grade 3 or Grade 4 per NCI CTCAE v5.0

All other abnormal laboratory findings will be captured via laboratory CRF pages and noted in shift tables.

Abnormal assessments (e.g., ECGs) that are judged by the Investigator as clinically significant will be recorded as AEs or SAEs if they meet the definitions as defined in [Section 11.1](#).

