**Investigational product, dosage and mode of administration:**

GC4419 is formulated as a clear solution at a concentration of 9 mg/mL in 26 mM sodium bicarbonate-buffered 0.9 wt. % saline for parenteral administration (drug product). GC4419 will be presented in single use vials, one vial per day. Vials will be filled with 11 mL of GC4419, of which 10 mL be added into a 250 mL bag of normal saline, for daily IV administration over 60 minutes. GC4419 will be administered concurrent with daily fractions of IMRT (2.0-2.2 Gy) to a total of 60-72 Gy over 7 weeks, plus cisplatin administered 100 mg/m^2 once every three weeks for 3 doses or 40 mg/m^2 once weekly for 6-7 doses (Investigator's choice).

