Cisplatin is administered concomitantly with IMRT by either a q3weekly or weekly schedule. Recent literature reviews (Sturtz, Wouters et al. 2017; Jacinto, Co, et al. 2017) have found no differences in tumor outcomes or mucositis between the two schedules. A randomized trial in the adjuvant (post-operative) setting (Noronha, Joshi, et al. 2018), in which 87% of patients enrolled had squamous cancer of the oral cavity, cited superior progression-free survival for the q3weekly arm, with no difference in mucositis. However, the weekly dose of cisplatin in that study was  $30 \text{ mg/m}^2$ . Other reports (Stojan, Vermorken et al. 2015; Nguyen-Tan, Zhang et al. 2014) have described a relationship between total cisplatin dose and overall survival in combination with RT for HNC, with a target cumulative cisplatin dose of  $200 \text{ mg/m}^2$  or greater now appearing indicated as standard of care to obtain improved survival with RT/cisplatin over RT alone. This threshold could be missed with weekly cisplatin doses  $< 40 \text{ mg/m}^2$ . In the present trial, cisplatin doses of  $100 \text{ mg/m}^2$  by the q3week schedule, and  $40 \text{ mg/m}^2$  by the weekly

schedule, will be required. The risk of severe OM may not be different according to cisplatin schedule, and no such difference was demonstrated in a subset analysis from GT-201 (data not shown). Either regimen will be accepted as within the IMRT/cisplatin standard of care for the patient population to be enrolled in the present study.

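### Section 11.2.3 makes a laboratory abnormality that delays cisplatin an AE, but has no criterion for one that ends cisplatin while GC4419 continues

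*Combined protocol and SAP*

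**What the plan says.** Section 11.2.3 sets a closed list: "Laboratory abnormalities should only be recorded in the Adverse Event section of the CRF if at least one of the following criteria is met". The five criteria, in order, are:

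1. "Meets the criteria of an SAE"
2. "Resulted in a dose reduction and/or delay in the administration of GC4419, IMRT, and/or cisplatin"
3. "Treatment is initiated for the abnormality"
4. "Investigational product was discontinued"
5. "Grade 3 or Grade 4 per NCI CTCAE v5.0"

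Any other abnormal laboratory finding goes to the laboratory CRF pages and the shift tables.

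The investigational product is GC4419. The synopsis names it as such, and the synopsis section headed "Investigational product, dosage and mode of administration" describes no other product as investigational.

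The primary endpoint (Section 5.2) has two parts: the frequency, duration and severity of AEs and SAEs, and the incidence and shifts of clinically significant laboratory abnormalities. Section 10.1.2 has the investigator mark each abnormal value as clinically significant or not.

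**The concern.** The second criterion names all three treatments; the fourth names only GC4419. Because the list gives discontinuation its own line, a reader cannot safely take reduction or delay to include stopping. The result is perverse: the milder consequence for cisplatin creates an AE record and the heavier one may not.

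The primary objective is the safety of GC4419 given with cisplatin and IMRT, and Section 12.2 says the data will feed a safety database of 300 subjects. A laboratory change that ends cisplatin is relevant to that objective. Without an AE record it has no relatedness assessment (Section 11.3) and none of the AE fields, including action taken (Section 11.4). It also does not reach the incidence tables for all treatment-emergent and treatment-related AEs (Section 12.4). A Grade 1 or 2 entry in a shift table does not show that the value ended cisplatin.

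**Working it through.** The plan gives no figure on this point, so the check is to run the rule through each case.

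**Case examined.** A laboratory abnormality of Grade 1-2, not serious and not treated, in a subject still receiving GC4419. Criteria 1, 3 and 5 are not met by construction, so recording depends on criteria 2 and 4.

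**Link between IMRT and GC4419.** Sections 6.2 and 8.6 and footnote 19 of the Schedule of Assessments bar GC4419 on a day without IMRT and resume it only when IMRT resumes. A permanent stop of IMRT is therefore also a stop of GC4419. No such link exists between cisplatin and GC4419.

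| Cisplatin | IMRT | Criterion met | AE record |
|---|---|---|---|
| unchanged | unchanged | none | no |
| delayed or reduced | unchanged | 2 | yes |
| **stopped, no earlier change** | **unchanged** | **none** | **no** |
| unchanged | delayed or reduced | 2 | yes |
| unchanged | stopped | 4 (GC4419 stops too) | yes |
| delayed or reduced | delayed or reduced | 2 | yes |
| delayed or reduced | stopped | 2 and 4 | yes |
| stopped | delayed or reduced | 2 | yes |
| stopped | stopped | 4 | yes |

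Of the eight combinations in which some action is taken, one goes unrecorded: cisplatin stopped with IMRT and GC4419 continuing.

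**Can that case arise?** Yes. Section 9.1 leaves cisplatin toxicity to institutional and ASCO guidelines and investigator judgment. It does not tie stopping to Grade 3-4, nor does it require a delay or reduction first. On the three-weekly schedule the third and last dose falls in Week 7 (Table 2; the body-surface-area footnote in Appendix 1). Leaving out that dose is not a delay, and not clearly a dose reduction.

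**How complete is the IMRT cover?** The exception is an IMRT stop after GC4419 has already ended. For a full GC4419 course that means after dose 35. Planned fractions run from 60 / 2.2 = 27.3, so 28, up to 72 / 2.0 = 36. At 70 / 2.0 = 35 fractions the two courses end together. A planned course exceeds 35 fractions only near 72 Gy at 2.0 Gy.

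**Scale.** At full enrolment each unrecorded subject is 1 / 70 = 1.4% of the analysis set for the AE term concerned. The documents give no count to multiply this by.

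**The case against.** The strongest case on the other side has four parts.

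- **The value is not lost.** It remains in the laboratory CRF and the shift tables. If marked clinically significant, as a value that ends cisplatin ordinarily would be, it counts in the laboratory part of the primary endpoint. This stands. A reader might infer that such events drop out of the primary endpoint altogether, and the documents do not support that. What is missing is the AE record and the link to the cisplatin stop.
- **The conditions are narrow.** Seriousness, treatment, Grade 3-4, or an earlier delay or reduction of any of the three treatments each trigger recording. A dose first held and then abandoned is already covered. This stands and limits the size.
- **Other text may fill the gap.** A site could read omitted doses as a reduction, and Section 11.2.2 asks for all AEs at any grade. This stands only in part. Section 11.2.3 is the specific rule for laboratory findings and narrows the general one, and it does not say that stopping counts as reduction. Sites could differ.
- **A change here could affect pooling.** The recording rules of the other GC4419 studies are not in the documents, so this can be neither confirmed nor dismissed. It is a reason to report any difference, not to keep the gap.

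A reader might also infer that stopping IMRT escapes the list in the same way. It does not while GC4419 is being given, because GC4419 stops with it.

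**Conclusion.** The gap is real but confined to cisplatin. An untreated, non-serious Grade 1-2 laboratory abnormality that ends cisplatin, with no earlier delay or reduction and with GC4419 continuing, need not be recorded as an AE, although one that only delays cisplatin must be. The gap works in one direction: it can lower AE frequency and cannot raise it.

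The size cannot be estimated from the documents. It is probably small, since several conditions must hold together. The conclusion assumes that sites apply the list literally and do not treat a stop as a reduction.

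Three stronger readings are not supported:

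- That a sizeable share of subjects would be missed. No rate of cisplatin stopping is given, and the same AE term will usually also be reached through other criteria in other subjects.
- That the 200 mg/m² cumulative cisplatin target in Section 6.2.2 bears on this. That passage concerns survival, and its remark that "This threshold could be missed with weekly cisplatin doses" is about weekly doses under 40 mg/m², not AE recording.
- That closing the gap would show whether GC4419 adds to cisplatin toxicity. The study is open-label with no reference therapy and descriptive safety summaries. Better capture improves the description but does not supply a comparison.

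**What to change.** Amend the second criterion in Section 11.2.3 to read: *Resulted in dose reduction, delay, omission or permanent discontinuation of GC4419, IMRT and/or cisplatin*. Delete the fourth criterion, which is then redundant, and align the CRF guidance. Naming IMRT also removes the small exception after GC4419 has ended. Replacement of cisplatin need not be listed, because Section 9.1 already rules out substitution. If the sponsor means cisplatin discontinuation not to be a recording criterion, the section should say so and give the reason.

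This changes data recording only and no treatment decision. The cost is one line of protocol text, the CRF guidance and a few more Grade 1-2 laboratory AEs. The pooled safety analysis should note any difference from the recording rules of the other studies.
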